3.2 Current Treatment for COVID-19

Currently, there is no cure or preventive vaccine for COVID-19. Several clinical trials are ongoing and investigating e.g. antiviral and immunomodulatory agents in the search for urgent, safe, and effective treatment of COVID-19 infection as well as vaccines for prophylactic treatment of COVID-9 infection (WHO). April 1., 2020, 260 trials investigating COVID-19 are listed at www.clinicaltrials.gov. The standard of care is primarily organ support depending on disease severity and complications (ICNARC 2020).

3.3 Investigational Medicinal Product

The investigational medicinal product (IMP) Compound 21 (C21), is a potent and selective angiotensin II (AngII) type 2 receptor (AT₂R) agonist presented as 50 mg capsules for oral administration.

C21 is a first-in-class, low molecular weight, orally available high affinity AT₂R agonist in development for COVID-19 and interstitial lung diseases, including idiopathic pulmonary fibrosis (IPF). The AT₂R, which can be viewed as an activator of a tissue-protective natural arm of the human body, is mainly expressed in embryonic tissue and, under normal conditions, only at low levels in most tissues in healthy adults (Steckelings et al., 2005; de Gasparo et al., 2002). However, the AT₂R is relatively highly expressed in the adult human lung (Human Protein Atlas), and can be upregulated during repair and regeneration (see e.g. Akishita et al., 1999).

The Renin Angiotensin System (RAS) is an important hormone system that regulates blood pressure, fluid, and electrolyte balance, and several other physiological processes. In the RAS cascade, the hormone angiotensinogen is converted to angiotensin I (AngI) by the enzyme renin, and AngI is then converted to the powerful vasoconstrictor AngII by angiotensin-converting enzyme (ACE). AngII functions through 2 specific receptor types, Angiotensin II Type 1 Receptor (AT₁R) and AT₂R which have opposing roles (Azushima et al., 2020).

The AT₁R mediates the classical actions of AngII, including constriction of blood vessels, sodium retention, and cell growth. However, abnormal AT₁R activation contributes to the pathogenesis of cardiovascular and renal diseases such as hypertension, myocardial infarction, heart failure, different fibrotic diseases as well as the "cytokine storm" causing acute respiratory distress syndrome (ARDS) in COVID-19 (Henderson et al., 2020). Conversely, activation of AT₂R causes dilatation of blood vessels and inhibition of inflammation, apoptosis, and fibrosis, and is thus considered to play a beneficial counter-regulatory role to the effects of AT₁R activation (Matavelli and Siragy, 2015). The natural ligands/agonists of AT₂R, Ang 1-7 and Ang 1-9, are the products of angiotensin-converting enzyme 2 (ACE2), a homologue to ACE, cleaving AngII and AngI, respectively (Guignabert et al., 2018). Interstingly, both ACE2 and AT₂R have been shown to protect mice from severe acute lung injury induced by acid aspiration or sepsis (Imai et al., 2005), and C21 has been shown to significantly reduce pulmonary inflammation in different animal models of acute lung injury by reducing pro-inflammatory cytokines such as IL-6 and TNF (Bruce et al., 2015; Menk et al., 2018; Rathinasabapathy et al., 2018).

ACE2 has been identified as the functional SARS-CoV receptor for cellular entry and replication, both *in vitro* (Li et al., 2003) and *in vivo* (Kuba et al., 2005). It is also known that such infection

Vicore Pharma AB Version: 2.0 Trial ID: VP-C21-006 Date: 14-Aug-2020

results in downregulation of ACE2 (Zhang et al., 2020). Because ACE2 protects against inflammatory lung injury, the SARS-CoV-mediated ACE2 downregulation is believed to contribute to virus-induced lung pathologies (Kuba et al., 2005) by a reduction of inhibitory control over toxic AngII and several pathological complications such as ARDS. More recently, it was shown that ACE2 is also the cellular receptor for SARS-CoV-2, the COVID-19 pathogen (Zhou et al., 2020), and it has been suggested that the interaction between ACE2 and CoV-1/CoV-2 (which is not seen with other less harmful corona viruses) may explain the shift in corona virus morbidity and mortality.

Taken together, Vicore's findings and the fact that the RAS plays a key role in the development of COVID-19 suggest that C21 may have a role in the treatment of the disease by directly activating AT₂R downstream of ACE2 and thus counteracting the deranged ACE2/ACE imbalance in the infected state.

3.4 Preclinical Safety

C21 has undergone an extensive nonclinical safety and toxicology evaluation including safety pharmacology, single, and repeated dose toxicity up to 13 weeks in rat, dog, and, cynomolgus monkey, genotoxicity, and phototoxicity studies. The key findings from the safety pharmacology studies and toxicology studies are presented in Table 3.

I abla 4	LIMMONU.	At KAY	Sataty and	OVION	logy Findings
1 AIII 1	SIIIIIIII V	III I X E V .	3 211		
I WOIL O	Dullilling ,	UI ILU , L	Juict, min	I UMICU	IUC I III MIIICO

	Rat		Dog		Cynomolgus Monkey	
Findings	Effect Dose	No Effect Dose	Effect Dose	No Effect Dose	Effect Dose	No Effect Dose
	(mg/kg)	(mg/kg)	(mg/kg)	(mg/kg)	(mg/kg)	(mg/kg)
Increased blood	n a	n.a.	11)	n o	n o	30
pressure	n.a.	11.a.	1 /	n.o.	n.o	50
Increased QTcR	n o	n 0	25 ¹⁾	15	n 0	30
interval	n.a	n.a	23 /	13	n.o	50
Increased PR	n o	n 0	$10^{1)}$	1	n 0	30
interval	n.a	n.a	10 /	1	n.o	50
Lens opacities	20	6	n.o.	25	n.o	30

n.a., not analysed; n.o., not observed; ¹⁾only observed in single dose telemetry trial.

In the rat, the main toxicological finding was an irreversible uni- or bilateral eye opacity after 13 weeks of treatment with C21 at doses of 20 and 60 mg/kg/day. The lenticular changes seemed to progress after cessation of the treatment. Lens opacity or lenticular changes were not observed in either dog or cynomolgus monkey and are therefore thought to be specific to the rat species.

Other findings observed in rats after treatment of C21 at doses up to 60 mg/kg/day for 4-13 weeks included reversible histopathological changes and/or higher organ weights of the liver, the adrenal, the ovary, the pituitary, and the thyroid gland. The no observed adverse effect level (NOAEL) in rats was determined to be 6 mg/kg/day in the 13-week study.

Vicore Pharma AB Version: 2.0 Trial ID: VP-C21-006 Date: 14-Aug-2020

In the dog, daily doses of 30 mg/kg/day C21 for 14 days were tolerated but were associated with small reductions in food intake and body weight, salivation, and emesis. In a 4-week toxicity study, no signs of toxicity were detected at doses up to 25 mg/kg/day but increases in blood pressure were observed in males administered 25 mg/kg/day. In the 13-week study, only marginal increases in blood pressure were observed after administration of 15 mg/kg/day and these were considered non-adverse as all values remained within the normal biological variation range.

Other findings in dogs after administration of 15-25 mg/kg/day for up to 13 weeks included small reversible changes in faecal consistency, decreased food consumption and an associated reduction in body weight gain, mild haemoconcentration (both sexes), slightly elevated monocyte count (males) and fibrinogen levels (both sexes), increased overnight urine volumes and an associated reduction in urine specific gravity (females).

In safety pharmacology studies, cardiovascular effects of C21 treatment were observed in Beagle dogs. The main findings were increased blood pressure and electrocardiography (ECG) aberrations. Increases in systolic and diastolic arterial pressure were observed at doses of 1 to 25 mg/kg in a single dose telemetry study and in a 4-week toxicity study only at the highest dose of 25 mg/kg/day. Effects on ECG were observed at single doses of 10 and 25 mg/kg in the dog telemetry study and consisted of PR and QT/QTcR (QT interval with Rautaharju's correction) prolongations, atrioventricular block I and II, and isolated premature ventricular contractions. These ECG aberrations could well be explained by the increase in blood pressure. In a 4-week dog toxicity study of C21 (up to 25 mg/kg/day), no ECG changes were observed.

In cynomolgus monkeys, treatment with 100 mg/kg/day C21 for 5 days resulted in emesis, slightly reduced body weight, excessive salivation, and liquid faeces. No test item related-findings were observed during the in-life ophthalmic investigations or after microscopic evaluation of the eyes at doses up to 30 mg/kg/day after 13 weeks of dosing. Administration of C21 at dose levels of 10-30 mg/kg/day in cynomolgus monkey was associated with excessive salivation, liquid faeces, and isolated areas of squamous skin. In addition, an increase in absolute and relative liver weight was observed in males, however this effect was probably a secondary effect due to hepatic P450 induction. The NOAEL in cynomolgus monkey was determined to be 30 mg/kg/day in the 13-week study.

There are no indications of mutagenic, genotoxic or phototoxic potential of C21.

For further details, please refer to the current Investigator's Brochure.

3.5 Clinical Safety

Safety and tolerability of C21 have been evaluated in three phase 1 trials of which 2 trials are completed (C21-001-16, C21-002-16) and 1 trial is in the reporting phase (C21-003 [preliminary data]). During these trials, C21 was evaluated in single ascending dose (SAD) and multiple ascending dose (MAD) trials at doses up to 200 mg twice daily for up to 8 days in healthy subjects and at doses up to 100 mg daily for up to 8 days in obese subjects. These trials included 83 subjects receiving at least 1 dose of C21.

Vicore Pharma AB Version: 2.0 Trial ID: VP-C21-006 Date: 14-Aug-2020

C21 was rapidly absorbed in all 3 trials with median t_{max} ranging from 20 to 60 min. The plasma concentration of C21 increased with dose in a dose-dependent (C21-003) or nearly supraproportional manner (C21-001-16, C21-002-16). Little or no accumulation of C21 was observed after 8 days of dosing. The exposure of C21 was substantially decreased under fed conditions as compared to fasted conditions (C21-003). The maximal plasma concentration (C_{max}) and area under the curve (AUC_{0-∞}) were reduced in a statistically significant manner and were 6.5 and 2.3 times lower, respectively, in the fed state when compared to the fasted state. In addition, median t_{max} was delayed by approximately 35 min in presence of food. These findings indicate a strong interaction with food.

Levels of the main metabolite of C21 in plasma, M1, were also quantified during the trials. M1 was rapidly formed across the trials and median t_{max} was reached a little later than for C21, ranging from 75 to 150 min. The plasma concentration of M1 also increased with dose in a nearly supraproportional manner. Little or no accumulation of M1 was observed after 8 days of dosing.

Across the trials, C21 was generally well tolerated at daily doses up to 200 mg, whereas doses of 200 mg twice daily (400 mg daily) for 8 days resulted in reversible alopecia in 6 out of 6 subjects occurring within 2 weeks after end of dosing and improving within 8 weeks after end of dosing (C21-003). The observed alopecia was considered related to C21-treatment and is possibly due to a secondary pharmacological effect of stimulation of the AT₂R.

The most frequently reported treatment-emergent adverse events (TEAE) related to C21 treatment was headache. Other TEAEs related to C21 treatment included dizziness, nausea, and fatigue that were reported by 2 subjects and pruritus, rash, vomiting, and diarrhoea that were reported as single events. One incidence of syncope of moderate intensity was reported as being related to C21 treatment (100 mg C21; C21-002-16) and one incidence of presyncope was observed and assessed as related to C21 treatment (100 mg C21; C21-002-16).

One episode of clinically significant PR prolongation was reported in 1 subject's ECG, recorded 1 hour after intake of 3 mg C21 (C21-001-16). This event was assessed as related to C21 treatment. However, a causal relationship with C21 treatment could not be confirmed or excluded and at this stage, it cannot be excluded that C21 could cause slowing of atrioventricular conduction (= PR prolongation) in susceptible individuals, although it is considered unlikely with a documented first and second degree atrioventricular block in the subject 1 month after the treatment period and given the reassuring telemetry findings within the recent phase 1 trial (C21-003) that C21 treatment did not affect ECG values.

There were no clinically significant abnormal findings in the safety laboratory parameters that were considered to be related to C21 treatment and no clinically significant findings or dose-related trends in blood pressure, heart rate, and ECG except for the above mentioned PR prolongation.

No serious adverse events (SAEs) or deaths observed during the 3 phase 1 trials.

In addition, a phase 2a trial in subjects with Raynaud's phenomenon secondary to SSc (SSc-RP) to show proof of mechanism of C21 on vasodilation is currently ongoing.

For further details, please refer to the current Investigator's Brochure.

Vicore Pharma AB
Version: 2.0
Trial ID: VP-C21-006
Date: 14-Aug-2020

3.6 Rationale for Trial

There is no cure or effective specific therapeutics for treating patients with COVID-19. A 51% mortality has been reported in the UK for patients in critical care (ICNARC 2020). The standard of care is primarily focussed on organ support such as respiratory failure. A safe and effective treatment is urgently needed to reduce mortality and improve clinical disease outcome such as from ARDS which is thought to manifest from the exuberant cytokine storm associated with the adaptive stage of the disease.

The current clinical trial is the first investigation of C21 in patients infected with COVID-19. Data from the trial will guide and support the design of further clinical investigations of C21 in this indication.

3.7 Rationale for Trial Design

Given the urgent need for effective medicines in COVID-19, proof of concept for C21 is sought within this randomised, double-blind, placebo-controlled phase 2 trial evaluating the safety and efficacy in subjects with COVID-19 infection who have been hospitalised and are not requiring mechanical invasive or non-invasive ventilation. The aim is to intervene early in order to prevent more serious complication such as ARDS and/or mechanical ventilation.

Approximately 150 subjects will be randomised in a 1:1 schedule to receive either standard of care + placebo or standard of care + C21 200 mg daily (100 mg *b.i.d.*[bis in die; twice daily]) for 7 days.

Rationale for the primary endpoint is supported by several very recent publications that have shown that CRP is an indicator of COVID-19 progression predicting severe disease (e.g. Li et al., 2020; Tan et al., 2020; Wang et al, 2020) and mortality (Ruan et al., 2020).

Data from the trial will guide the design of further clinical investigations of C21 in this indication.

3.8 Rationale for Dose and Dosing Regimen

C21 is being developed for oral treatment of COVID-19. COVID-19 is a viral infection that spreads easily and may cause severe respiratory illness that is potentially life-threatening and represents a huge challenge to the health care system.

The results of the phase 1 healthy subject trials for C21 (C21-003; preliminary data) indicate an acceptable safety and tolerability profile for the 100 mg b.i.d. dose. The risks of C21 in adults are considered primarily related to reversible alopecia seen at the higher dose of 200 mg b.i.d. In the recent phase 1 trial, the 100 mg b.i.d. dose administered for 8 days did not cause any hair loss. Alopecia is therefore not considered to present any significant safety risk to subjects in this trial.

In the recent phase 1 trial (C21-003), 100 mg b.i.d dosing prolonged the duration of the plasma concentration at the rapeutic relevant levels. After oral administration, C21 was rapidly absorbed. On day 8, median t_{max} was 0.33 hours after each dose post-dose, and C21 was only measurable in plasma until 4-6 hours after the first and second dose. Lower doses than 100 mg b.i.d. may not provide maximal efficacy benefit.

Vicore Pharma AB Version: 2.0 Trial ID: VP-C21-006 Date: 14-Aug-2020

The most recent information on the natural course of hospitalised COVID-19 patients, indicate that these patients generally deteriorate within 48 hours and are either discharged or taken into intensive care within 7 days. Hence, it is currently believed, that 7 days of treatment with C21 is a sufficient treatment duration for a conclusive first trial in this population.

Overall, the safety profile of C21 as available from preclinical data and from the phase 1 trials is interpreted as favourable for further study of the intended indication 'Treatment of COVID-19'.

3.9 Risk-Benefit Assessment

Currently, there is no cure or preventive vaccine for COVID-19 and the disease has a mortality rate of 51% for patients in critical care (ICNARC 2020).

The risks to subjects in the present trial will be reduced by using a C21 dosing regimen (100 mg b.i.d for 7 days), which has been evaluated in the recently completed phase 1 trial (C21-003) and found to have an acceptable safety profile.

The risks of treatment with C21 are primarily considered related to alopecia. However, in the phase I trial, alopecia occurred only in subjects who received 200 mg *b.i.d.* for 8 days. Regrowth of the hair observed to date provides reassurance that any such an effect is reversed on cessation of treatment.

There is a hypothetical risk of cataract, given lens opacities seen in one species, the rat; however, the dog and the non-human primate showed no evidence at all of this finding, increasing the likelihood that the effect is rat specific. In the recently conducted phase 1 trial (C21-003), no effect was demonstrated on the lens of subjects exposed to 100 mg *b.i.d* or 200 mg *b.i.d* for 8 days.

In the present trial, any potential risks will be minimised by strict compliance with the eligibility criteria. All subjects participating in the trial will be followed closely by medically qualified staff throughout the trial period (see Section 2 and Section 6.1). Adverse events (AEs) will be carefully documented, and the subjects will receive relevant treatment should they occur.

Furthermore, the protocol defines withdrawal criteria (see Section 5.4) to secure the safety of subjects with severe progression of disease. If the physician judges it necessary for the subject to receive mechanical ventilation or a different treatment during the trial period, the subject will be withdrawn from the trial and receive relevant treatment.

Based on the above, it is considered ethically justifiable to include subjects in the present trial, as the potential benefits of C21 are judged to balance possible disadvantages connected with participation in the trial.

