### 6.4 Data Presentations

The data will be summarised in tabular form by treatment group apart from disposition of subjects, prior and concomitant medications and background and demographic data which will be summarised by treatment group and overall subjects.

Treatment groups will be presented in the following order using these labels:

- SoC + C21 100 mg b.i.d
- SoC + Placebo

Listings will be sorted by treatment group, site and subject number and date/time of assessment.

Data will be summarised and listed using the following analysis sets:

	Enrolled	RAS	FAS	PPAS	SAS
Tables	
 
• Disposition
 
	
 
• Withdrawal
 
	
 
• Demography
 
• Efficacy
 
	
 
• Demography
 
• Efficacy (primary endpoint only)
 
	
 
• Demography
 
• Prior and concomitant medications
 
• Medical history
 
• Exposure
 
• Safety
 

Listings	
 
• Completion/ withdrawal
 
• Eligibility
 
	
 
• Protocol deviations
 
• Analysis sets
 
• Demography
 
• Medical history
 
• Disease under investigation
 
• Hospitalisation
 
• Visit dates
 
• Randomisation
 
• Efficacy
 
• Biomarkers
 
			
 
• Prior and concomitant medications
 
• Safety
 
• IMP administration
 
• Exposure
 

1. Demography will be summarised using the FAS and repeated for the PPAS and SAS where the analysis sets differ for at least 1 subject. If either of these analysis sets are identical to the FAS the summary will not be presented.

Only scheduled post baseline data will be tabulated, post-baseline repeat/unscheduled assessments will not be included in tables, although they will be listed and in particular all clinically significant values will be noted.

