### **6.10.1 Primary Endpoint**

The primary endpoint is the change in CRP from baseline to the mean of the last two non-missing scheduled assessments occurring during the seven day treatment period (Visits 2 to 8 and/or withdrawal). For subjects who do not complete treatment, the assessments up to and including the next-non missing assessment following the final administration of study treatment will be considered for inclusion in the mean.

The baseline CRP assessment is defined as the Visit 2 value supplied by the central laboratory where this assessment occurs prior to the first administration of study treatment. Should the Visit 2 assessment be taken after first administration of study treatment or be missing, the Visit 1 value will not be used and the baseline CRP assessment will remain missing. This avoids potential differences amongst local

laboratories that supply the Visit 1 CRP data following the protocol amendment of 14 August 2020. If necessary, the incorporation of Visit 1 local laboratory CRP values may be investigated post-hoc to support any conclusions of the CSR.

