### Imputation

Subjects with a missing baseline assessment or no post-baseline assessment of CRP will not be imputed and will not be included in the analysis.

Post-baseline assessments up to and including the next non-missing assessment (including those at or after the withdrawal assessment) following the final treatment administration will be considered as the treatment period for inclusion in the mean. The mean of their last two non-missing scheduled assessments during the treatment period, or a single CRP value where the subject has only completed one post-baseline CRP assessment, will be carried forward to represent state at the end of trial.

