### Sensitivity Analysis

A sensitivity analysis will be conducted using the mean of the last two non-missing post-baseline values during the treatment and follow-up periods (up to and including Visit 9). If there is only one post-baseline value then this value will be used. This approach is expected to be conservative as it includes a time period when patients in the active treatment arm are potentially untreated.

The analysis will be a repeat of the ANCOVA described above.

Further sensitivity analyses may be considered post-hoc.

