13.3 Efficacy Analysis

13.3.1 Efficacy Endpoint Analysis

The primary endpoint will be the change in CRP from baseline to the average of the last 2 assessments during the treatment period. For early withdrawn subjects (any cause) the last computable average or value (if only one) will be carried forward to represent state at end-of-trial. CRP data will be summarised by day and treatment including the change from baseline. Treatments will be compared using an analysis of covariance (ANCOVA) model with fixed factor treatment and baseline CRP as covariate. Estimated treatment difference will be given with 90% confidence intervals and associated, two-sided, p-value. Subjects will be evaluated both with respect to the FAS and the PPAS populations.

Secondary (continuous) endpoints such as body temperature and pre-specified laboratory values and biomarkers will be summarised by visit and for the change over trial by descriptive statistics. The change from baseline will be compared using similar ANCOVA models as the primary endpoint.

The number of subjects not in need of oxygen or not in need of mechanical ventilaton will be compared between treatments using a logistic regression model adjusting for treatment. Estimated treatment difference will be given as an odds ratio with 90% confidence intervals and associated, two-sided, p-value. For early withdrawn subjects the status as assessed on last day in the treatment will be used.

The time to need of mechanical invasive or non-invasive ventilation will be summarised by treatment group and compared between groups using the log-rank test. Subjects not in need of mechanical ventilation will be censored at last day in treatment period.

The time on oxygen supply (for those not needing mechanical ventilation) will be summarised by treatment group. For subjects withdrawing from the trial (for instance due to worsening), imputation assuming oxygen need will be made. Treatment groups will be compared using the Wilcoxon rank sum test.

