13.3.3 Statistical/Analytical Issues

13.3.3.1 Missing Data

The imputation of last value (average) carried will be used for analysis if subject is early withdrawn.

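### The CRP sensitivity analysis to Visit 9 has no scheduled follow-up CRP, so it is not conservative for the reason given and cannot test the carry-forward of early values

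*Combined protocol and SAP*

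**What the plan says.** **Schedule.** Protocol Table 2 and Section 8.1.2 place CRP at Visits 1 to 8, with an additional sample for subjects who leave IMP early. Section 6.5.3 lists CRP among the withdrawal assessments. Visit 9 (Section 6.5.4) may be a telephone contact and lists no blood sampling. After an early IMP stop, Section 5.4.1 asks for the withdrawal assessments and Visit 9, and names nothing in between.

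**Primary handling.** Protocol 13.3.1: "For early withdrawn subjects (any cause) the last computable average or value (if only one) will be carried forward to represent state at end-of-trial". Protocol 13.3.3.1 repeats this in general form: "The imputation of last value (average) carried will be used for analysis if subject is early withdrawn". Under SAP 6.10.1, non-completers contribute assessments "up to and including the next-non missing assessment following the final administration of study treatment". The mean of the last two of these, or a single value, "will be carried forward to represent state at the end of trial". Subjects without a valid baseline or any post-baseline CRP are left out.

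**Planned check.** SAP 6.10.1: "A sensitivity analysis will be conducted using the mean of the last two non-missing post-baseline values during the treatment and follow-up periods", with Visit 9 as the end of the window and the same ANCOVA. The SAP expects the result to be conservative because the window covers time when the active arm may be off drug. Any further sensitivity analysis is post hoc.

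**Unscheduled values.** SAP 6.4 says that "post-baseline repeat/unscheduled assessments will not be included in tables".

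**Withdrawal narrative.** Protocol 3.9, in the risk-benefit text, says that if the physician sees a need for "mechanical ventilation or a different treatment during the trial period, the subject will be withdrawn from the trial and receive relevant treatment".

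**The concern.** A sensitivity analysis of a carry-forward rule is useful only if it brings in data that the rule leaves out. Here the added window, from the end of treatment to Visit 9, contains no scheduled CRP. The analysis will therefore tend to agree with the primary result because it uses nearly the same values.

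Early stopping is foreseeable. Discharge and need for ventilation both end IMP (Protocol 5.4.1), and Section 3.8 expects these patients to be discharged or in intensive care within 7 days. Both events are related to the course of the disease. The risk is a study report that cites agreement with a supposedly conservative analysis as evidence that carrying early values forward did not matter.

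**Working it through.** **The plan's own figure.** The documents give no number for this point. The stated power does reproduce: the standard error is 60 × √(2/75) = 9.80 mg/L, 25/9.80 = 2.55, and 2.55 − 1.645 = 0.91, so power is about 81.8% (81.5% with the t distribution) against the stated approximate 80%. It has no bearing on what follows.

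**Inputs.** Visits are one day apart in the treatment period (Protocol Table 1), so Visit k is Day k − 1 and Visit 2 is Day 1. Scheduled post-baseline CRP in the treatment period is Visits 3 to 8: 6 per subject, or 6 × 150 = 900 in all.

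**Completers.** The primary analysis uses Visits 7 and 8, with mean day (6 + 7)/2 = 6.5. The Visit 9 analysis finds no later scheduled value and uses the same two. The shift is 0 days.

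**Early stoppers.** Let d be the day of the last dose and W the withdrawal sample. Assume that W is a separate draw on Day d or d + 1; the protocol does not fix its timing.

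- If the Day d visit sample precedes the last dose, both analyses use {d, W}, with mean day d to d + 0.5. The shift is 0.
- If the visit sample follows the last dose, the primary window closes at that sample and uses {d − 1, d}, with mean day d − 0.5 (the single value d when d = 2). The Visit 9 analysis uses {d, W}.
- For a stop on Day 1, the Visit 2 sample is the baseline, so W is the only post-baseline value in both analyses.

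| Stop at | d | Primary mean day | Gap to 6.5 | Visit 9 analysis mean day | Gap to 6.5 | Shift |
|---|---|---|---|---|---|---|
| Visit 2 | 1 | 1.0–2.0 | 4.5–5.5 | 1.0–2.0 | 4.5–5.5 | 0 |
| Visit 3 | 2 | 2.0–2.5 | 4.0–4.5 | 2.0–2.5 | 4.0–4.5 | 0–0.5 |
| Visit 4 | 3 | 2.5–3.5 | 3.0–4.0 | 3.0–3.5 | 3.0–3.5 | 0–1.0 |
| Visit 5 | 4 | 3.5–4.5 | 2.0–3.0 | 4.0–4.5 | 2.0–2.5 | 0–1.0 |
| Visit 6 | 5 | 4.5–5.5 | 1.0–2.0 | 5.0–5.5 | 1.0–1.5 | 0–1.0 |
| Visit 7 | 6 | 5.5–6.5 | 0–1.0 | 6.0–6.5 | 0–0.5 | 0–1.0 |

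The Visit 9 analysis leaves most of the gap in place for stops up to Visit 5, and all of it for a stop at Visit 2.

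**Samples needed to close the gap.** Continuing to Day 7 adds 7 − d samples, or one fewer if W falls on Day d + 1. The maximum is 6, for a stop on Day 1.

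**The case against.** **The schedule is partly an inference.** No sentence cancels the remaining visits after an IMP stop. Section 8.1.2 calls the withdrawal sample additional, leaving IMP is separate from leaving the trial (5.4.1, 5.4.2), and the SAP imputation text allows for assessments at or after withdrawal. If daily visits did continue, the Visit 9 analysis would already use CRP taken off IMP. That stands as a caveat. But 5.4.1 and 6.5.3 require only the withdrawal assessments and Visit 9, and SAP 6.10.2.5 imputes oxygen status after the last dose. Even if visits continued, there would still be no CRP between Visit 8 and Visit 9.

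**The sensitivity text omits the word scheduled.** An unscheduled follow-up CRP could therefore enter, and the rule in SAP 6.4 concerns tables, not model input. This is correct, and it is why the point is limited to scheduled data. Values taken only where care happened to prompt them would be selective, so they do not support the stated rationale.

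**This is an on-treatment endpoint by choice.** The last two treatment-period values are the endpoint definition in a 7-day proof-of-concept trial, and ventilation and death are followed to study completion in other sensitivity analyses. This is a fair reason to leave the primary analysis alone. It does not make the Visit 9 analysis informative.

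**The remedy is partial.** Discharged subjects would keep early values, and those still in the facility are likely to be the sicker ones. Enrolment was planned to end in Q3 2020, so an amendment may reach few subjects. Both limits stand.

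**Conclusion.** The point holds for the sensitivity analysis and its rationale. On scheduled data the shift in value date is 0 days for completers and 0 to about 1 day for early stoppers, whose primary value can be dated up to 5.5 days before a completer's. The analysis cannot show whether the result depends on carrying early values forward. This rests on the natural reading of 5.4.1 and 6.5.3 and on W falling on Day d or d + 1.

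A reader might infer more than the documents support:

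- **That the primary result is biased.** The documents give neither the frequency of early stopping nor its effect in mg/L. Bias between arms requires stopping to differ by arm. Blinding limits this, but a real drug effect on recovery could still produce it.
- **That carry-forward is the only planned handling.** SAP 6.10.1 excludes subjects without a baseline or any post-baseline CRP, and a PPAS repeat is planned.
- **That Protocol 3.9 removes from the trial anyone given another standard-of-care drug.** Section 3.9 is narrative and refers to 5.4. Under 5.4.1 ventilation stops IMP and Visit 9 is kept, 7.8.1 permits standard-of-care medication, and investigator medical judgement is already a listed ground. The 3.9 sentence is a minor wording mismatch, and none of the figures above depend on it.

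**What to change.** 1. **SAP 6.10.1, sensitivity analysis.** Remove the statement that the analysis is conservative. State that no CRP is scheduled at Visit 9 or after the withdrawal sample, and that agreement with the primary analysis will not be reported as evidence of robustness. This needs no new data and can be done before database lock, by when the SAP is to be approved (Protocol 13).
2. **Protocol 5.4.1 and 6.5.3.** State that subjects who stop IMP, remain in the hospital or facility and have not withdrawn consent keep daily CRP to calendar Day 7.
3. **SAP.** Pre-specify one sensitivity ANCOVA on the last two CRP values to Day 7 regardless of IMP status. Report it as only partly treatment-policy, because discharged subjects have no later values.
4. **Protocol 3.9.** Align the sentence with 5.4.1 as an editorial change.

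The primary analysis and its carry-forward rule stay unchanged.

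**Cost.** Item 2 is a protocol amendment, needing regulatory and ethics approval under Section 10.1 if substantial; SAP Section 1 allows the SAP to follow. If 5% to 20% of 150 subjects stop early (an assumption) and each needs the maximum of 6 samples, the upper bound is 150 × 0.05 × 6 = 45 to 150 × 0.20 × 6 = 180 samples, against 900 planned. The analysis itself is one more run of the same model. Nothing is recovered for subjects already finished or discharged. If the amendment comes too late to be worthwhile, item 1 should still be made.
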